7.8.2 Withdrawal from Study

The Investigator may withdraw subjects from the study for many reasons, including but not limited to the following:

- subject noncompliance (e.g., did not follow instructions)
- subject lost to follow-up
- safety reasons (e.g., AEs, ADEs, SAEs)
- if the Investigator or the Sponsor stops the study for any reason and decides to withdraw subject(s) from the study
- concurrent illness
- any other significant reason identified by the Investigator.

For each case, information will be obtained in the source document and the eCRF, detailing circumstances leading to the withdrawal. Data collected upon point of withdrawal will be included as study data.

Subjects who drop out or are withdrawn will not be re-entered into the study at a later date.

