9.1.12 Discontinued Subjects

Discontinued subjects are those who voluntarily discontinue participation, who are withdrawn for reasons of safety, who are LTFU, or meet any of the criteria listed in Section 7.8 of this protocol. Where possible, a full Exit Visit should be completed for all subjects who discontinue the study early. Where consent is withdrawn, the date and any reason given for discontinuation should be captured, at a minimum.

Finally, if appropriate, the Investigator will also advise the subject of subsequent therapy and/or procedures necessary for their medical condition.

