10.2 ANALYSIS POPULATIONS

The following study populations and analysis sets will be defined.

- Full analysis set (FAS): following the Intention to Treat principle including all randomized patients who were recruited into the study and attended at least one post-surgery assessment. This analysis population includes all randomized patients in the groups to which they were randomly assigned, regardless of their adherence with the entry criteria, regardless of the treatment they actually received, and regardless of subsequent withdrawal from treatment or deviation from the protocol.
- Per protocol set (PP): including all patients in the full analysis set who have no significant protocol deviations and met the inclusion/exclusion criteria.
- Safety analysis set (SAF): including all patients who have received the study device.

CONFIDENTIAL AND PROPRIETARY

Study Protocol	Smith-Nephew
A Prospective, Multi-center, Randomized Controlled	Number:
Study to Evaluate the Safety and Efficacy of ARCR	REGENETEN.2020.01
augmented with REGENETEN™ Bioinductive Implant	Version: 2.0, 08 Dec
System in Full-thickness Tears (large or massive) Repair	2021
	Page: 71 of 134

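### Section 7.8.2 lets an unblinded investigator end a subject's study follow-up for noncompliance or other reasons, with nothing that secures the 6-month MRI afterwards

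*Combined protocol and SAP*

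**What the plan says.** Section 7.8.2 opens with "The Investigator may withdraw subjects from the study for many reasons, including but not limited to the following". The list includes noncompliance ("subject noncompliance (e.g., did not follow instructions"), safety ("safety reasons (e.g., AEs, ADEs, SAEs"), concurrent illness and a catch-all, "any other significant reason identified by the Investigator". The circumstances must be documented in the source and the eCRF. Two rules follow: "Data collected upon point of withdrawal will be included as study data" and "Subjects who drop out or are withdrawn will not be re-entered into the study at a later date".

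Other sections bear on this:

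- Section 8.2.2: the study is not blinded.
- Section 8.3.1: the primary endpoint is the cumulative 6-month retear rate, read as Sugaya Type IV or V on MRI. MRI is scheduled at 3 months (Section 9.1.6) and 6 months (Section 9.1.7).
- Section 10.2: the full analysis set (FAS) follows the intention-to-treat principle and keeps randomized patients with at least one post-surgery assessment, "regardless of subsequent withdrawal from treatment or deviation from the protocol".
- Section 10.4.1: the primary analysis uses the FAS and per-protocol sets. No handling of a missing 6-month MRI is given.
- Section 9.1.12: "Where possible, a full Exit Visit should be completed for all subjects who discontinue the study early". It does not name MRI or a time point.
- Section 7.8.4: further data collection is barred where the subject withdraws consent. It does not address withdrawal by the investigator.

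**The concern.** The study treatment is delivered once, in theatre, and Section 7.8.1 deals separately with not implanting the device. Once surgery is over there is no treatment to stop, so a Section 7.8.2 withdrawal acts mainly on the outcome data.

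The person deciding knows the arm, and two of the grounds could be linked to the outcome or to the arm:

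- Failure of the repair or retear is a listed potential complication (Section 4.4.4), and adverse events are a ground for withdrawal.
- The recommended rehabilitation guidance in Section 6.2 is headed for the device arm only, while Section 9.1.3 tells sites to use standard of care and/or that guidance. What counts as not following instructions may therefore differ by arm.

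If those withdrawn retear more often than those retained, and the loss differs between arms, an analysis of observed outcomes is biased. Loss unrelated to outcome still costs power, and Section 11 states no allowance for it.

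**Working it through.** **1. The plan's own figure.** Section 11 gives 260 subjects (130 per arm) for 15% versus 30% retear, 80% power and 5% significance (two-sided, Section 10.1), with a Lan-DeMets O'Brien-Fleming boundary and one interim look at 50%.

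n per arm = [1.960 × √(2 × 0.225 × 0.775) + 0.842 × √(0.30 × 0.70 + 0.15 × 0.85)]² / 0.15² = 121.

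The boundary (z = 2.963, then 1.969) inflates this by 1.004, to 122 per arm or 244 in total. So 260 is not reproduced from the stated inputs. An unstated loss of about 6% would explain it (122 / 0.94 = 130). The point here does not depend on 260. Group-sequential power at 130 per arm is 82.4%.

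**2. Loss unrelated to outcome.** The same power calculation with fewer outcomes per arm:

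| Loss per arm (assumed) | Power |
|---|---|
| 0% | 82.4% |
| 5% | 80.4% |
| 10% | 78.3% |
| 15% | 76.0% |
| 20% | 73.4% |

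**3. Selective loss with no true effect.** Assumptions, none given in the documents: a true rate of 30% in both arms, a fraction w withdrawn, retear risk q among them, and no outcome contributed by anyone withdrawn. The observed rate in an arm is (0.30 − w × q) / (1 − w).

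With q = 0.60:

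- w = 0.08: (0.30 − 0.048) / 0.92 = 27.4%
- w = 0.02: (0.30 − 0.012) / 0.98 = 29.4%
- w = 0.10: (0.30 − 0.060) / 0.90 = 26.7%
- w = 0.03: (0.30 − 0.018) / 0.97 = 29.1%

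The value of q drives the result, so a range is needed. False difference in points (positive favours the device):

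| q among withdrawn | Device 8%, control 2% | Device 10%, control 3% | Device 2%, control 8% |
|---|---|---|---|
| 30% | 0.0 | 0.0 | 0.0 |
| 45% | 1.0 | 1.2 | −1.0 |
| 60% | 2.0 | 2.4 | −2.0 |
| 100% | 4.7 | 5.6 | −4.7 |

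At q = 60%, 10% versus 3% loss raises the chance of a falsely significant device benefit from 2.5% to about 6% (normal approximation, single look at z = 1.96).

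**4. Equal loss.** At 5% in both arms, if the withdrawn carry the same q in both arms, the two observed rates are equal and there is no bias under the null. If q is 60% in the device arm and 30% in control, the observed rates are (0.30 − 0.03) / 0.95 = 28.4% and 30.0%: a false 1.6 points, with a false-positive chance of 4.6% against 2.5%.

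**5. Fragility near the boundary (extreme case).** With 27/130 versus 39/130 retears, z = 1.71, not significant. If three device-arm subjects who would have been retears are lost, 24/127 versus 39/130 gives z = 2.07, past the final bound of 1.969.

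**The case against.** Several points on the other side stand in whole or in part.

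- **Permission is not practice.** Section 7.8.2 says the investigator may withdraw, asks for a significant reason under the catch-all, and requires documentation. A reader might infer that follow-up will be ended selectively, or that any reason suffices. The documents support neither, although the list is expressly open-ended.
- **The FAS wording is not contradicted.** A reader might infer a direct conflict between Sections 7.8.2 and 10.2. Section 10.2 speaks of withdrawal from treatment and of deviation; it is silent on withdrawal from the study. The withdrawn subject remains in the set. The gap is an outcome that may be missing, with no stated handling.
- **Some outcomes survive.** A retear seen on the 3-month MRI is kept and should count under the cumulative definition in Section 8.3.1, although Section 10.4.1 describes retears at the 6-month visit. A full Exit Visit could be read to include MRI, because the 24-month visit (Section 9.1.9), which carries the Exit Visit form, lists one. Section 9.1.12 says neither this nor when the scan should fall. Step 3 assumes no such rescue, so it is at the high end for the loss rates used.
- **The mechanism is assumed.** Noncompliance could mean missed visits rather than ignored rehabilitation advice, and a doubled retear risk need not follow. The q = 30% row shows that the bias then vanishes.
- **Sensitivity analysis helps.** It might be thought that later analysis can do nothing. A tipping-point analysis can bound the effect of missing outcomes, and Section 10 defers detail to a later SAP. It cannot recover a scan never taken.

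The independent MRI reader (Section 9.2.12) does not answer the point, since that reader cannot read a scan that was not done.

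**Conclusion.** The point holds as a gap that should be closed. A stated rule allows the primary outcome to go missing, at the discretion of someone who knows the arm, for subjects whose deviations the FAS is meant to tolerate. Nothing else in the protocol secures the 6-month MRI after such a withdrawal.

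On the central assumptions the false difference is 2.0 to 2.4 points, the larger being about a sixth of the 15-point target (2.4 / 15 = 0.16). It runs from zero to 5.6 points across the retear risks tried, and its direction follows the imbalance. Equal loss is safe only if the withdrawn carry the same risk in both arms. All of this rests on assumed loss rates and risks; the documents contain no evidence of actual imbalance.

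**What to change.** In Section 7.8.2, separate protocol deviation from end of follow-up:

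- Record noncompliance as a deviation. The per-protocol set in Section 10.2 already excludes significant deviations, so withdrawal is not needed for that purpose.
- For any subject who has not withdrawn consent and can be contacted, including those with an adverse event or concurrent illness, continue scheduled visits and seek at least the 6-month MRI where the investigator judges it safe. Leave the investigator's safety grounds in place.
- In Section 9.1.12, state that the Exit Visit includes an MRI if the 6-month scan has not been done.
- In Section 10.4.1 or the SAP, state how a missing 6-month outcome is handled, and add a tipping-point sensitivity analysis by arm.

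The principle is already in the protocol: Section 9.1.13 keeps a subject who becomes pregnant in follow-up while omitting contraindicated procedures.

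The cost is an amendment with the signatory, ethics and regulatory approvals that Section 15 requires, and some extra retention effort for visits already in the schedule. An MRI at an exit visit outside the schedule would be an added scan.

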7.8.3 Subject's Withdrawal of Consent to Participate in Study

Study participation is voluntary, and subjects may withdraw at any point during the study without giving their reason for doing so. Where subjects withdraw consent, the Investigator should make a reasonable effort to ascertain the reason(s), while fully respecting the subject's privacy. The reason for withdrawal will be recorded in the eCRF and source documents.

CONFIDENTIAL AND PROPRIETARY

Study Protocol	Smith-Nephew
A Prospective, Multi-center, Randomized Controlled	Number: REGENETEN.2020.01
Study to Evaluate the Safety and Efficacy of ARCR augmented with REGENETEN™ Bioinductive Implant	Version: 2, 08 Dec 2021
System in Full-thickness Tears (large or massive) Repair	Page: 44 of 134

7.8.4 Use of Data Following Withdrawal

In cases where the subject withdraws consent, the data collected up to the point of withdrawal may be used, but no additional data for that subject may be collected.

CONFIDENTIAL AND PROPRIETARY

Study Protocol	Smith-Nephew
A Prospective, Multi-center, Randomized Controlled	Number:
Study to Evaluate the Safety and Efficacy of ARCR	REGENETEN.2020.01
augmented with REGENETEN™ Bioinductive Implant	Version: 2, 08 Dec 2021
System in Full-thickness Tears (large or massive) Repair versus ARCR alone	Page: 45 of 134

8. STUDY DESIGN

8.1 STUDY DESIGN

This study is a prospective, multi-center, randomized, controlled clinical study intended to evaluate the safety and efficacy of ARCR augmented with REGENETEN versus ARCR alone in the treatment of full-thickness tears of the rotator cuff (large or massive ≥3 cm in AP or ML according to Cofield classification) including a single group of revision repair subjects. This clinical trial is supporting the registration of a medical device in China and will support the post market clinical follow up in Europe, Australia and New Zealand after market approval and reimbursement to relevant countries and therefore is required to follow the requirements of relevant regulations issued by NMPA, PMDA MHRA, EMA, TGA, Medsafe, HealthCanada or FDA.

Study duration is planned to take approximately 42 months (18-month enrollment and 24-month follow-up).

The subjects meeting the inclusion/exclusion criteria specified in the protocol will receive either ARCR augmented with REGENETEN or ARCR alone. Subjects enrolled into the revision repair subject group will receive ARCR augmented with REGENETEN.

[figure not shown]
For primary hypothesis a total of up to 260 subjects (130 ARCR augmented with REGENETEN; 130 ARCR alone) and additionally up to 40 revision repair subjects if applicable, for sub-group analysis are planned to be included in up to 30 study sites. Using a group sequential design, a formal interim analysis will be conducted once 50% of the planned 260 subjects reach the 6-month follow-up at which point a sample size re-estimation will be performed along with options considered to terminate early for efficacy or futility or to increase the sample size.

The clinical follow-up evaluation will be performed preoperatively (Baseline), 2 weeks, 6 weeks, 3, 6, 12, and 24 months after surgery, respectively.

CONFIDENTIAL AND PROPRIETARY

Study Protocol	Smith-Nephew
A Prospective, Multi-center, Randomized Controlled	Number:
Study to Evaluate the Safety and Efficacy of ARCR	REGENETEN.2020.01
augmented with REGENETEN™ Bioinductive Implant	Version: 2, 08 Dec 2021
System in Full-thickness Tears (large or massive) Repair versus ARCR alone	Page: 46 of 134

[figure not shown]
Figure 8.1-1 Study Flowchart - Main Arms

CONFIDENTIAL AND PROPRIETARY

Study Protocol	Smith-Nephew
A Prospective, Multi-center, Randomized Controlled	Number:
Study to Evaluate the Safety and Efficacy of ARCR	REGENETEN.2020.01
augmented with REGENETEN™ Bioinductive Implant	Version: 2, 08 Dec 2021
System in Full-thickness Tears (large or massive) Repair versus ARCR alone	Page: 47 of 134

Figure 8.1.2 - Revision Repair Arm

8.2 ALLOCATION AND BLINDING

8.2.1 Treatment Allocation

Enrolled primary subjects entering the randomized controlled part of the study will be randomized to either ARCR augmented with REGENETEN or ARCR alone. The randomization will be a 1:1 blocked scheme using an external online system to conceal allocation. The online system will assign a Randomization ID only after the subject meets all eligibility criteria. Details of the blocked scheme will be presented within the SAP.

Enrolled revision repair subjects will not be randomized. All subjects will be treated with ARCR augmented with REGENETEN.

CONFIDENTIAL AND PROPRIETARY

Study Protocol	Smith-Nephew
A Prospective, Multi-center, Randomized Controlled	Number:
Study to Evaluate the Safety and Efficacy of ARCR	REGENETEN.2020.01
augmented with REGENETEN™ Bioinductive Implant	Version: 2, 08 Dec 2021
System in Full-thickness Tears (large or massive) Repair versus ARCR alone	Page: 48 of 134

8.2.2 Blinding

This is not a blinded study.

8.3 STUDY ENDPOINTS

8.3.1 Primary Endpoint

The primary study endpoint is the cumulative 6 months retear rate after full-thickness ARCR augmented with REGENETEN versus ARCR alone. Failure is defined as Sugaya Type IV or V retear/recurrence (full-thickness discontinuity seen on both coronal and oblique sagittal MRI images).

8.3.2 Secondary Endpoints

The secondary study endpoints are:

- The cumulative 3, 12, and 24 months retear rate after full-thickness ARCR augmented with REGENETEN (confirmed on MRI) versus ARCR alone;
- Overall performance of full-thickness ARCR augmented with REGENETEN versus ARCR alone at Baseline and at 3, 6, 12 and 24 months assessed by:
 - Oxford Shoulder Score (OSS),
 - Western Ontario Rotator Cuff (WORC)/Chinese version WORC (C-WORC) Index,
 - Constant-Murley Score,
 - Subjective shoulder value (SSV),
 - o EuroQol 5 Dimension 5 Level (EQ-5D-5L) Score,
 - Patient satisfaction Questionnaire,
 - Pain, Visual analog scale (VAS) Score (additionally at baseline, 2 weeks, 6 weeks, 3 months and 6 months);
- MRI Tendon Findings in ARCR augmented with REGENETEN versus ARCR alone postoperatively at Baseline, 3, 6, 12 and 24 months including:
 - Sugaya score,

CONFIDENTIAL AND PROPRIETARY

Study Protocol	Smith-Nephew
A Prospective, Multi-center, Randomized Controlled	Number:
Study to Evaluate the Safety and Efficacy of ARCR	REGENETEN.2020.01
augmented with REGENETEN™ Bioinductive Implant	Version: 2, 08 Dec 2021
System in Full-thickness Tears (large or massive) Repair versus ARCR alone	Page: 49 of 134

- Goutallier grading,
- o Total tendon thickness, tendon length,
- Size of retear (anteroposterior [AP]/mediolateral [ML]),
- Shape of retear;
- Outcome of Return to Work Questionnaire in ARCR augmented with REGENETEN versus ARCR alone (additionally at 2 and 6 weeks);
- Cumulative duration of opioid use in ARCR augmented with REGENETEN versus ARCR alone at 2 weeks postoperatively;
- Total operative time in ARCR augmented with REGENETEN versus ARCR alone;
- Sling type and mobilization time in ARCR augmented with REGENETEN versus ARCR alone.

8.3.3 Other Endpoints

Other Study Endpoints are:

- To assess safety and efficacy as summarized in secondary endpoints in at-risk groups (diabetics, smokers, hypertensive, heavy laborer, age > 65 years) after full-thickness ARCR augmented with REGENETEN versus ARCR alone;
- To assess safety and efficacy as summarized in secondary endpoints in revision repair subjects group after full-thickness ARCR augmented with REGENETEN;
- To collect health economic evidence in ARCR augmented with REGENETEN versus ARCR alone:
 - Aggregate health care utilization costs,
 - Number of unscheduled visits,
 - Reoperation rate,
 - Reoperation type, type of surgery,
 - Time of baseline operation to time of reoperation,
 - Level of service (LOS): In the case of reoperation: How many nights did the subject spend in the hospital as a result of the surgery? 0, 1, 2, 3, 4, 5, >5.

CONFIDENTIAL AND PROPRIETARY

Study Protocol	Smith-Nephew
A Prospective, Multi-center, Randomized Controlled	Number:
Study to Evaluate the Safety and Efficacy of ARCR	REGENETEN.2020.01
augmented with REGENETEN™ Bioinductive Implant	Version: 2, 08 Dec 2021
System in Full-thickness Tears (large or massive) Repair versus ARCR alone	Page: 50 of 134

8.3.4 Safety Endpoints

Safety endpoints include the collection of the following events:

- All adverse events (AEs) occurring from the time of subject enrollment until study termination or study completion including intra-operative adverse events,
- Device Deficiencies.

8.4 METHODS USED TO MINIMIZE BIAS AND MAXIMIZE VALIDITY

8.4.1 Multi-center

The samples from multi-center are more representative than those from single center, and the latter may lead to deviation of study results due to its systematic errors. The required number of cases can be enrolled in a shorter period, and the samples are more representative and the results are more generalizable.

In this study, subjects will be enrolled at multiple sites, utilizing up to 30 sites globally. This will reduce the effect of observer bias that might arise at any one investigational site as well as maximize the diversity of subjects treated.

8.4.2 Randomization

Subjects meeting all inclusion/exclusion criteria will be randomly allocated into any of two study groups in a 1:1 allocation ratio. Blocked randomization will be used to balance this allocation ratio by investigational site and overall. Randomization will be conducted through an online system. Randomization will occur and a treatment will be assigned only when subject has signed the ICF and satisfied all study eligibility criteria.

8.4.3 Measurement Consistency

For the primary endpoint (cumulative 6 months retear rate on MRI) of each site, consistency measurement should be performed. Failure is defined as Sugaya Type IV or V retear/recurrence

CONFIDENTIAL AND PROPRIETARY

Study Protocol	Smith-Nephew
A Prospective, Multi-center, Randomized Controlled	Number:
Study to Evaluate the Safety and Efficacy of ARCR	REGENETEN.2020.01
augmented with REGENETEN™ Bioinductive Implant	Version: 2, 08 Dec 2021
System in Full-thickness Tears (large or massive) Repair versus ARCR alone	Page: 51 of 134

(full-thickness discontinuity seen on both coronal and oblique sagittal MRI images). There is a preference for 3.0Tesla MRI imaging, wherever available. 1.5Tesla systems will only be approved if 3.0Tesla MRI is not available. Images will be obtained as described in the image acquisition protocol (IAP).

8.4.4 Imaging Evaluation

For further details of imaging evaluation, refer to Image Review Guidelines. Imaging observation indicator is a reasonable and necessary indicator to evaluate the success rate of retear rates, MRI grading, and tendon thickness. To reflect the importance of imaging change over time, measurements should be made before surgery as well as 3, 6, 12, and 24 months after surgery.

8.4.5 Screening of Subjects

In order to eliminate selection bias, the Investigators will continuously screen all subjects. Subject recruitment continues until the completion of recruitment of 260 RCT subjects and up to 40 revision repair subjects.

8.4.6 Investigator Training

Prior to the clinical trial, the clinical research associate (CRA), coordinating with the persons in charge of the study sites, will train the Investigators on the study protocol, making sure they are familiar with the use of investigational medical device, and implement subject enrollment strictly in accordance with the inclusion criteria and exclusion criteria, conduct relevant examinations according to the protocol requirements, also master all new device-related information found during the clinical trial, thus to minimize the interferential factors.

8.4.7 Clinical Trial Monitoring

Detailed monitoring requirements will be documented in the Clinical Monitoring Plan for this study. The monitor is selected and appointed by the Sponsor to conduct a regular on-site monitoring visit, making sure that all contents in the study protocol are strictly followed. The

CONFIDENTIAL AND PROPRIETARY

Study Protocol	Smith-Nephew
A Prospective, Multi-center, Randomized Controlled	Number:
Study to Evaluate the Safety and Efficacy of ARCR	REGENETEN.2020.01
augmented with REGENETEN™ Bioinductive Implant	Version: 2, 08 Dec 2021
System in Full-thickness Tears (large or massive) Repair versus ARCR alone	Page: 52 of 134

source documents are inspected to ensure consistent contents with the eCRF. Monitoring visits will be conducted at the start, during and at the closure of the clinical study in accordance with Smith+Nephew standard operating procedures (SOPs) and the Clinical Monitoring Plan.

CONFIDENTIAL AND PROPRIETARY

Study Protocol	Smith-Nephew
A Prospective, Multi-center, Randomized Controlled	Number:
Study to Evaluate the Safety and Efficacy of ARCR	REGENETEN.2020.01
augmented with REGENETEN™ Bioinductive Implant	Version: 2, 08 Dec 2021
System in Full-thickness Tears (large or massive) Repair versus ARCR alone	Page: 53 of 134

